### Patient Participants – Quantitative

English-speaking patients will complete a package of surveys regarding health and perceptions of cancer navigators. Patient demographics will be obtained to include age, race, ethnicity, sex and gender, marital status, primary language, birth country, employment, education level, household income, insurance and type, housing/shelter, food, transportation insecurity, and environmental safety.

Patient-reported outcomes will occur at baseline and 3-month follow-up. These outcomes will include the PROMIS Global Health (HR-QoL) scale (Hays et al., 2009) to ascertain health-related quality of life to assess physical, mental, and social health and the Patient Satisfaction with Logistical Aspects of Navigation Scale (PSN-L) (Carle et al., 2014) to assess satisfaction with the navigation program. Additionally, barriers will be measured by the barriers to cancer care assessment used in the NCI Patient Navigation Research Program (Freund et al., 2008).

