#### Recruitment of Patients

Patients undergoing screening as standard of care will have access to clinic-based educational materials, i.e. signage and pamphlets in English and Spanish on cancer screening, diagnosis and care and on the study opportunity.

As standard of care for patients who screen positive, a care navigator will be assigned. The care navigator will provide patients with study recruitment materials and information, ensuring patients are aware that study involvement does not impact care navigation or treatment.

After positive breast, lung, and/or prostate cancer screening in the field or at an emergency room or care facility, study team members will be informed of positive field screens. Patients with positive screens will be referred for confirmatory diagnostic testing and will receive guidance from care navigator and the financial navigator to set up appointments. A study team member will meet the potential participant at the site of diagnostic testing and/or at emergency departments or other urgent care sites to introduce the study and obtain informed consent for research activities.

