### **Statistical Analysis Plan**

#### **Primary Objective Analysis**

Patient-reported demographic characteristics will be analyzed using descriptive statistics associated with the **Reach** aim. To address the **Effectiveness** aim pre- and post-intervention barriers data and patient-reported outcomes will be analyzed using univariate, bivariate, and repeated measures analyses. Referral data will be

descriptively evaluated based on percent increase/decrease across the intervention. Qualitative data will be analyzed to determine the extent to which the **Adoption** aim was met. Analyses of the fidelity of the intervention, including timeliness and consistency will be documented as part of the **Implementation** aim. Finally, process-level descriptions, including the summation of monthly team meetings and direct communications with the Implementation Scientist of the community-focused multi-disciplinary navigation intervention will be used to assess the **Maintenance** aim.

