### **Data Collection and Follow-up for Withdrawn Subjects**

Participants who are withdrawn from the study for any reason will have their previous data included in summary reports (i.e., baseline characteristics) and pre-post comparison analyses up to the point of withdrawal unless they specifically request that their data be excluded from future use. They will be counted in the participant flowchart. A study team member will contact participants who do not complete the entire research study to find out the reason(s) to guide future program development and improvement.

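### Satisfaction with navigation (PSN-L) has no pre-intervention value, so its baseline-to-3-month difference should not count as Effectiveness evidence

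*Protocol*

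**What the plan says.** Under Patient Participants – Quantitative, the Protocol says that "Patient-reported outcomes will occur at baseline and 3-month follow-up". It names two instruments as these outcomes: PROMIS Global Health, for quality of life, and the PSN-L, which is included "to assess satisfaction with the navigation program". A barriers assessment is listed in addition. The PSN-L is not exempted from baseline. The table under Study Visits places baseline surveys at visit 2 and 3-month surveys at visit 4, without splitting them by instrument.

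Under Primary Objective Analysis, for the Effectiveness aim, "pre- and post-intervention barriers data and patient-reported outcomes will be analyzed using univariate, bivariate, and repeated measures analyses". The PSN-L is not exempted there either. The section on withdrawn subjects also speaks of "pre-post comparison analyses up to the point of withdrawal".

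Recruitment of Patients gives the order of events: "As standard of care for patients who screen positive, a care navigator will be assigned". The care and financial navigators help to arrange the confirmatory tests. For study entry, "A study team member will meet the potential participant at the site of diagnostic testing", or this happens at an emergency department or urgent care site.

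**The concern.** A pre/post comparison needs a first measurement that describes the patient without the intervention. Quality of life and barriers to care exist whether or not a navigator is involved. Satisfaction with navigation does not, because its object is the intervention itself.

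The study is not randomized and no comparator is described for the patient-reported outcomes. Within-patient change is therefore the main quantitative contrast that these data offer for Effectiveness. A change in PSN-L would be read that way, yet it can mislead in both directions. A patient who is pleased at first contact and still pleased at 3 months shows no change, even if navigation worked well. A patient who gives a cautious early answer and a warmer later one shows a gain that need not reflect any benefit.

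**Working it through.** The Protocol states no effect size, standard deviation, power or significance level for the PSN-L, and the patient sample is a convenience sample. There is no figure to reproduce, so the check sets the sections against each other.

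**Inputs**

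| Item | What the Protocol gives | Section |
|---|---|---|
| PSN-L timing | Baseline and 3 months, no exemption | Patient Participants – Quantitative; Study Visits |
| What it rates | The navigation program | Patient Participants – Quantitative |
| Analysis | Pre/post and repeated measures, under Effectiveness | Primary Objective Analysis |
| Start of navigation | At the positive screen, as standard of care | Recruitment of Patients |
| Consent | At diagnostic testing, or at an emergency or urgent care site | Recruitment of Patients |
| Baseline survey | Visit 2, after consent at visit 1; no interval stated | Study Visits |

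**Step 1: where baseline falls.** The navigator is assigned at the positive screen, and "The care navigator will provide patients with study recruitment materials and information". Contact with the navigator is therefore expected before consent, and the baseline survey follows consent. A patient who consents at diagnostic testing may already have had that appointment arranged. One who consents in an emergency department may have had much less.

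**Step 2: the two readings of baseline.** Write S0 for the baseline PSN-L, S3 for the 3-month PSN-L, and D = S3 − S0.

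1. *Baseline before any navigation.* There is no service to rate. S0 has no meaning, and neither does D.
2. *Baseline after first navigator contact.* S0 is an early rating of the service and S3 a later one. D describes how opinion moved during the service. It contains no state without the intervention, and S0 is taken after differing amounts of navigation in different patients.

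On neither reading is D an effect of the intervention.

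**Step 3: what D can and cannot show.** If a patient gives the same score s at both times, D = s − s = 0 whatever s is. A service rated consistently high and one rated consistently low both give D = 0. The level S3 separates them, and D does not.

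**Step 4: is this peculiar to the PSN-L?** For PROMIS and the barriers assessment, a survey before first navigator contact would give a true pre-intervention value. For the PSN-L, moving baseline earlier only turns reading 2 into reading 1. Timing cannot cure it.

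**Step 5: how far it reaches.** Research Design determines Effectiveness by monthly referral uptake against baseline. Dashboard and Records lists referral of positive screens and screening rates. Neither uses the PSN-L. The flaw sits in the patient-reported part that Primary Objective Analysis adds to the aim.

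**The case against.** **Many patients will have something to rate at baseline.** This stands. A reader might infer that baseline comes straight after consent and that the scale is then unanswerable. The Protocol gives only the order of visits, and navigation starts before consent. But an answerable score is still not a pre-intervention score.

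**The Protocol never states a PSN-L change score.** It lists several methods without assigning them to instruments, and the pre/post phrase could grammatically apply to the barriers data alone. That reading is possible. Two scheduled administrations, together with repeated-measures analysis named for patient-reported outcomes, make the wider reading the natural one. If the narrower one is meant, the text should say so. Assigning methods to scales can be left to an analysis plan. The timing of a questionnaire and the aim it serves are fixed here.

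**The 3-month level may already be covered.** A reader might infer that the interpretable quantity is not planned at all. The univariate analysis could supply it, so that inference fails. What is missing is any statement that the level, and not the change, is the PSN-L result.

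**The rest of Effectiveness is untouched.** Correct. It would be wrong to conclude that the whole aim is compromised.

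**Repeated satisfaction ratings have legitimate uses.** They serve the secondary goal on perceptions of navigators and the improvement cycles. Participants stay active only until diagnosis and a treatment plan, or until they decline care, so for some the early rating may be the only one. This is a good reason to keep the baseline score under another label.

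**A mislabelled baseline also affects PROMIS and the barriers data.** True if those surveys follow the start of navigation. It is a separate question of timing, which correcting the PSN-L does not settle.

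**Conclusion.** The point holds in a limited form. The PSN-L difference from baseline to 3 months is not an intervention effect and should not be counted as Effectiveness evidence. This is so whether baseline falls before or after first navigator contact.

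It affects all PSN-L pre/post contrasts and one of the two named patient-reported outcomes. No numerical size can be given, and the Protocol offers no basis for the direction of the distortion. The examples of high or cautious early answers illustrate what could happen; the scale's items and response options are not reproduced in the Protocol.

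The conclusion assumes that the pre/post and repeated-measures wording covers the PSN-L, and that the scale rates the study's navigation service, as the Protocol says. It deserves correction before surveys begin, because an analysis plan can relabel a baseline score but cannot change when it was collected.

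**What to change.** 1. **Primary Objective Analysis:** exclude the PSN-L from the pre/post Effectiveness comparison. State that the PSN-L result is its level and distribution at 3 months, after navigation has been used.
2. **Patient Participants – Quantitative:** preferably keep the baseline PSN-L, label it early (first-contact) satisfaction, report it descriptively, and say that it is not a pre-intervention value. Dropping it is the alternative, but may lose the only rating from patients who decline care or leave early.

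The cost is a few sentences in two sections. If the baseline PSN-L is kept, nothing changes in data collection; if it is dropped, there is one questionnaire fewer at baseline. The downside is that no PSN-L pre/post change is reported as an effect. Early and later ratings can still be shown side by side as a description of how satisfaction developed.

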### Patient Participants – Qualitative

Patients will be invited to participate in interviews regarding decision points in diagnostics and care. They will be invited to at least one, and up to five, interviews with a study team member. Interviews will be no longer than one hour each. Virtual interviews will take place via video conferencing software and will be recorded and transcribed electronically. In-person interviews will be recorded with a portable digital recording device and will be manually transcribed. An open-ended interview guide will be available in English and Spanish. Both versions will be IRB-approved prior to use. Questions regarding barriers and facilitators to cancer diagnosis and the care continuum will be addressed in addition to process and program feedback for improvement.

## Stakeholder Participants – Qualitative

Stakeholders will be invited to participate in interviews and/or focus groups about their knowledge, attitudes, and practices related to cancer screening processes, as well as the RE-AIM model dimensions. They will be invited to at least one, and up to five, interviews with a study team member. These will occur over the 12-month study period, alongside the monthly stakeholder focus group meetings. Interviews/focus groups will be no longer than one hour each. All stakeholder interviews/focus groups will take place via video conferencing software and will be recorded and transcribed electronically.

Questions will be asked to further the understanding of factors influencing reach, screening, and study recruitment (Reach), effectiveness and impact on outcomes (Effectiveness), and staff participation (Adoption), as well as implementation facilitators and barriers for screening, diagnosis, treatment, and clinical trials (Implementation). An open-ended interview guide will be available in English and Spanish.

Qualitative data gathering will inform timely actionable changes to improve cancer screening, identification, treatment, and outcomes. Other *ad hoc* groups will be formed as needed to address specific questions or concerns that arise in processes or from feedback.

## Data Management and Quality Plan

### Data De-identification

Participants will be added to the EDC system called REDCap using a unique participant identification number (PID). This PID is a code consisting of a combination of numerals and letters, which will serve as the identifier for this participant for this study. Access to the “link” between PIDs and participants’ identities will exist only in the Enrollment Log and the EDC, which can only be accessed by study team members.

Survey data will be exported from REDCap in Excel format. An Excel file used for analysis will be de-identified and only include the PIDs. The storage location will be secured and only accessible by study team members in the Microsoft OneDrive folder.

All interview data will have names deleted and replaced with a unique identifier for the participant.

The electronic health record data that is collected as part of a clinic visit will be added in a de-identified manner (i.e., by the PID) to the Excel file used for analysis and stored securely in the Microsoft OneDrive folder that is only accessible by study team members.

### Data Confidentiality, Storage, and Retention

The participants’ identities will be kept confidential to the extent permitted by the applicable laws and/or regulations and will not be made publicly available. If study results are published or presented, participants’ identities will not be revealed. Confidentiality will be maintained during and after the study.

Study documentation and data records will be stored as electronic records. All data are safeguarded so that only members of the study team have access to it via role relationship (electronic). The electronic data are maintained under AIT security controls. Email addresses of enrolled participants will be stored in the shared folder and will be retained for 7 years following study closure. Electronic de-identified data will also be kept in our database for 7 years. Paper records, if any, will be stored in a locked facility for 7 years.

For qualitative interviews, an interview transcript will be obtained using transcription from the Microsoft Teams recording. Alternatively, an audio file will be obtained through portable digital recording device and will be transcribed. A member of the research team will verify the accuracy of transcriptions. The recording and transcript of the interview on Microsoft Teams, as well as the original audio file on the portable digital recording device, will be deleted after transcription is complete and verified. Participants will be advised that Microsoft Teams saves a record of the meeting via the Chat feature indefinitely. Transcripts will be saved electronically on the personal protected drive of the qualitative researcher. All identifiable information will be deleted from transcripts and replaced with a unique identifier based on participant role, e.g. CRS Stakeholder 1; Provider 1.

### **Data Quality**

Participants will complete all surveys electronically through REDCap, and this data will be exported into an Excel file, limiting the need for transcription and potential errors to occur. Quality of qualitative data will be ensured by checking transcripts against recordings of focus groups and interviews.

### **Data Sharing**

N/A

### **Sample Size Determination**

Sample sizes for the qualitative data component of implementation research range between five and 10 key stakeholders to provide sufficient information power and saturation (Hamilton & Finley, 2019).

Sample size for patients will be a convenience sample based on the number of positive screens. Approximately 10% of those screened for breast cancer require follow-up diagnostics (Kumar et. al, 2020), 20% of those screened for lung cancer require follow-up diagnostics (Babar et. al, 2023) and 6-20% of those screened for prostate cancer require follow-up diagnostics (McFall & Smith, 2009).

### **Statistical Analysis Plan**

#### **Primary Objective Analysis**

Patient-reported demographic characteristics will be analyzed using descriptive statistics associated with the **Reach** aim. To address the **Effectiveness** aim pre- and post-intervention barriers data and patient-reported outcomes will be analyzed using univariate, bivariate, and repeated measures analyses. Referral data will be

descriptively evaluated based on percent increase/decrease across the intervention. Qualitative data will be analyzed to determine the extent to which the **Adoption** aim was met. Analyses of the fidelity of the intervention, including timeliness and consistency will be documented as part of the **Implementation** aim. Finally, process-level descriptions, including the summation of monthly team meetings and direct communications with the Implementation Scientist of the community-focused multi-disciplinary navigation intervention will be used to assess the **Maintenance** aim.

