## Research Intervention Description

The proposed intervention integrates cancer screenings at pop-up clinics located at community resource spots in partnership with well-established community-based organizations for the underserved, as well as in local emergency departments that serve this population. Currently, cancer screenings are offered as standard of care in primary care settings; however, this population rarely has access to primary care. Instead, this population often seeks episodic care for symptom management and does not benefit from preventive care services in primary care settings. Integrating cancer screenings into episodic care will be accomplished through a multi-faceted approach which includes leveraging a team of navigators to help connect those with positive screening results to community health resources, treatment financial advocacy, care coordination, and access to screening for clinical trials. Navigators will guide access to a continuum of care including diagnosis, treatment, and clinical trials.

National guidelines exist for primary care providers to conduct annual screenings to detect and treat common cancer tumors before they progress to systemic disease. These guidelines are not routinely followed in non-primary care settings, like pop-up clinics and emergency rooms. The study team will provide education to community-based healthcare providers on United States Preventive Services Taskforce Screening Guidelines for breast, lung, and prostate cancers. The USPSTF recommends annual screening for lung cancer with low-dose computed tomography (LDCT) in adults aged 50 to 80 years who have a 20 pack-year smoking history and currently smoke or have quit within the past 15 years. The USPSTF recommends biennial screening mammography for women aged 40 to 74 years. The USPSTF recommends that the decision to undergo periodic prostate-specific antigen (PSA)-based screening for prostate cancer should be an individual one among men aged 55 to 69 years. All participant-facing education materials will be reviewed and approved the Institutional Review Board (IRB) before use in the research study.

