### Inclusion Criteria

The inclusion criteria for patients will be the following:

1. Adult aged 18 or older
2. Seeking care at a CRS or emergency department
3. Meets criteria for lung, breast, and/or prostate cancer screening, as outlined below:
  - a. Lung cancer: Adults aged 50 to 80 years who have a 20 pack-year smoking history and currently smoke or have quit within the past 15 years
  - b. Breast cancer: Women aged 40 to 74 years
  - c. Prostate cancer: Men aged 55 to 69 years
4. Receives a positive screening result for lung, breast, and/or prostate cancer at a study site

The inclusion criteria for stakeholders will be the following:

1. Speaks English or Spanish through study interpreters
2. Able to attend 75% or more of scheduled meetings
3. Must be key individuals providing critical services to address food insecurity, employment assistance, government support, mental and physical health, and health education within identified Community Resource Spots, emergency departments, and urgent care centers.

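### No enrolled patient has a scheduled pre-intervention survey, so the pre- and post-intervention survey contrast under Effectiveness is change from enrollment to 3 months

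*Protocol*

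**What the plan says.** Under the Effectiveness aim, the protocol's Primary Objective Analysis section states that "pre- and post-intervention barriers data and patient-reported outcomes will be analyzed using univariate, bivariate, and repeated measures analyses".

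The intervention has two components in the Research Intervention Description. The first is screening: "The proposed intervention integrates cancer screenings at pop-up clinics located at community resource spots", with emergency departments also named. The second is navigation: "leveraging a team of navigators to help connect those with positive screening results to community health resources". The Primary Objective Analysis section itself speaks of a "community-focused multi-disciplinary navigation intervention".

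The Inclusion Criteria require of each patient: "Receives a positive screening result for lung, breast, and/or prostate cancer at a study site". Recruitment of Patients then says: "As standard of care for patients who screen positive, a care navigator will be assigned". It continues: "The care navigator will provide patients with study recruitment materials and information".

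The patient table under Study Visits puts consent at visit 1, baseline surveys at visit 2 and the 3-month surveys at visit 4. Patient Participants – Quantitative gives the same two time points for the patient-reported outcomes. These include PROMIS Global Health and PSN-L, which rates satisfaction with the navigation program. The same section adds a barriers instrument without timing it separately.

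**The concern.** A pre/post contrast analysed by repeated measures needs a value from each patient taken before the intervention reached that patient. The eligibility rule and the recruitment route suggest that the first survey comes too late for this. If so, the label promises a comparison that the visit schedule does not contain.

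What is at stake is interpretation. Change between two surveys, both taken after screening and navigator assignment, would be reported under Effectiveness as change from before to after the intervention. Any change before the first survey, such as barriers already eased by the navigator, would be missed. The later change would carry a meaning that it cannot support.

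**Working it through.** No figure in the protocol is at issue, so the check consists of putting the stated events in order.

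1. Screening at a study site (Research Intervention Description: part of the intervention).
2. Positive result (Inclusion Criteria: required for entry).
3. Care navigator assigned (Recruitment of Patients). Assignment follows the positive screen and does not depend on consent.
4. Navigator passes on the recruitment materials; the care and financial navigators help arrange diagnostic appointments (Recruitment of Patients).
5. Consent, visit 1, at a diagnostic, emergency or urgent care site (Recruitment of Patients, Study Visits).
6. Baseline surveys, visit 2.
7. 3-month surveys, visit 4.

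The handover of materials in step 4 must precede step 5. The appointment help is described before consent, but the protocol does not say how much of it each patient has had by then.

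Patient survey time points: 2 (steps 6 and 7). Scheduled before step 1: 0. Scheduled before step 3: 0.

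The result can be tested against different ideas of where the intervention starts:

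- Screening plus navigation, as the Research Intervention Description has it: starts at step 1, and baseline falls after it.
- Screening alone: starts at step 1, and baseline falls after it.
- Navigation alone, counted from assignment: starts at step 3, and baseline falls after it.
- Only the later navigation services (diagnostic, financial, treatment and trial linkage): baseline may precede much of this, but the protocol does not state the interval and does not define the intervention this way.

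**PSN-L.** A patient can rate the navigation program only after meeting it. Its baseline score is an early rating, not a pre-intervention value, whichever start is chosen.

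**Barriers instrument.** Its timing is not given separately, but the visit table has no survey other than those at baseline and 3 months.

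**Month-1 data.** Study Duration plans baseline data gathering in month 1 on screening knowledge, attitudes, practices, barriers and facilitators. Neither the respondents nor the instrument are named, and it is not described as a survey of the patients later enrolled. Such data could be compared with later patient data only as unpaired groups, so they cannot supply the pre value for a repeated measures analysis.

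**The case against.** The best defence is that assignment of a navigator is not delivery of navigation. Patients are approached for consent when referred for diagnosis, and some are met in an emergency or urgent care setting, perhaps soon after the positive screen. For them little navigation may precede baseline. This stands, and it is why no bias can be sized. It does not rescue the label: screening is also part of the intervention and precedes every survey, and patients met at the diagnostic site may already have had help with appointments.

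A second defence is that navigation is described as standard of care and so is not the intervention. The Research Intervention Description and the analysis section place it inside the intervention, and setting it aside would still leave screening.

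Third, the words pre- and post-intervention may modify only the barriers data. The grammar allows this. The barriers data would still lack a scheduled pre-intervention patient value, and the PSN-L remark would become a clarification.

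Fourth, Effectiveness rests mainly on other measures. That is correct: Research Design determines it by referral uptake against baseline, and the outcome list under Effectiveness contains only referral and screening measures.

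Some stronger readings are tempting but not supported:

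- A reader might infer that the withdrawal section repeats the error. It says only "pre-post comparison analyses up to the point of withdrawal" and does not mention the intervention, so it can simply mean baseline against follow-up.
- A reader might infer from the Randomization entry that there is no comparison group. That entry says only that randomization does not apply.
- A reader might call the contrast change under navigation. That is not accurate for everyone, since by 3 months some patients may have a negative diagnosis or have declined further care.

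**Conclusion.** The point holds for the patient-survey part of Effectiveness. On the protocol's own sequence, each enrolled patient has 0 scheduled surveys before the positive screen and navigator assignment. The available paired contrast therefore runs from enrollment to 3 months. This is a named contrast that the design cannot deliver, not a detail left for a separate analysis plan.

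It rests on the intervention including screening, navigation or both, as the protocol describes it, and on the visit table being the complete survey schedule.

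A reader might go further and infer that the survey change is biased in a particular direction, or that the whole Effectiveness evaluation fails. The documents support neither. The amount of navigation before baseline is not stated, and the referral-uptake and Healthy People 2030 measures do not use these surveys.

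**What to change.** In Primary Objective Analysis:

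- Describe the patient-survey contrast as *change from enrollment (after positive screen and navigator assignment) to 3 months*, and do not present it as a pre/post effect of the intervention under Effectiveness.
- Report PSN-L as the level at each time point and the change between them.
- If the month-1 data in Study Duration are the intended pre value for barriers, say so, name the respondents and the instrument, and analyse them as unpaired.

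The cost is a change of wording in one section and, if month 1 is intended, one clarification in Study Duration. No new data are needed. The downside is a less favourable Effectiveness claim from the surveys.
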